Study Protocol and Statistical Analysis Plan

Sound Quality Comparisons with Different Hearing Aid Couplings and Venting Systems

Version 2.0

04/11/2023

NCT05180630

Protocol Title

Sound Quality Comparisons with Different Hearing Aid Couplings and Venting Systems

1 Background

When achieving optimal success with a hearing aid client, clinicians often have to manipulate coupling to adapt to patient's complaints. For example, more occluded coupling allows for less direct sound, al-lowing for a heavier balance of the HI's DSP algorithms relative to the environment. However, this occlusion often comes with client com-plaints of an unsatisfactory perception of their own voice. When the ear canal is occluded, it eliminates the ability for sound to transfer out of the ear canal, altering the ear canal acoustics and creating a change in perception of the user's own voice. This change in perception is often described as the user's voice being too loud, "boomy", or "hollow" (Winkler et al. 2016). Commonly, this becomes a process of trial and error for HCPs. A dynamic vent offers a potential solution for these situations. The mechanical operation of a dynamic vent allows for an occluded coupling in situations such as media streaming, but allows for an open coupling in situations where a more open coupling will suffice. The dynamic nature of a dynamic vent allows for the ear canal acoustics to adapt to the environment. For example, when streaming media, a closed position does not allow low frequencies to transfer out of the ear canal as they would with open fittings. Contrarily, in guiet environments, a vent that remains open allows for a more natural perception of the user's own voice.

Research has been conducted at NAL (sponsored by Sonova) as well as internally, to investigate sound quality and occlusion of a dynamic vent compared to other coupling options. However, previous research has investigated custom earmolds with various degrees of venting as comparators to a dynamic venting system. In the United States, it is customary to use universal domes (open, closed, vented, power, etc.), assuming gain is not a limiting factor and domes provide adequate retention. This research intends to identify significant perceptual difference in terms of sound quality, and occlusion, when a dynamic venting system is compared to universal open domes and vented domes.

2 Objectives

The primary objective of this study is to evaluate an active venting system across domains of sound quality and occlusion. More specifically, researchers hypothesize that a dynamic venting system will provide better streaming sound quality than coupling achieved with an open dome. Additionally, researchers hypothesize that a dynamic venting system will provide better quality of their own voice (less occlusion effect) than with coupling achieved with vented domes.

3 Description of the investigational device

The overall intended purpose of the device is to amplify and transmit sound ot the ear and thereby compensate for impaired hearing. The dynamic receiver features a mechanically

switching vent that is seamlessly steered by the automatic operating system of the hearing aid. It combines the hearing performance of the a closed fit with the comfort of an open fit.

4 Design of the clinical investigation

This confirmatory study will have 3 conditions across two tasks. One task will be investigating streaming sound quality and the other will investigate own voice perception (occlusion effect). The sample population will be of 15-20 human subjects. The order of conditions will be counterbalanced and the participants will be blinded to the conditions.

5 Risks and benefits of the investigational device and clinical investigation

There are minimal risks associated with both the investigational device and participating in the clinical investigation. Identified risks are no greater than those associated with the daily use and wear of approved, available hearing aids. The device used presents non-significant risk per FDA.

The benefits of participating in the investigation include the possibility of hearing sounds that have not been previously heard, such as speech and environmental sounds, which may improve communication in daily life. Subjects may experience the benefit of personal satisfaction for participating in research to improve hearing instrument technology. Subjects will also be compensated for their time in participating in this study.

There are no known or anticipated risks to subject hearing ability associated with participation in this study. All sounds used in this study will be presented at safe listening levels. While using hearing aids, the following are possible occurrences:

•Cerumen impaction

•Ear discomfort, pain or soreness

•Sweat or moisture accumulation in the ear canal or pinna

•A feeling of pressure or fullness in the ear

•Itching, blisters, or sores in the ear canal or pinna

•Headache

•Redness of tissue

The research personnel will review these risks with the subjects and answer any questions they have. Hearing aids are not a significant risk investigational device as defined in the FDA 21 CFR 812.3(m).

6 Endpoints

Primary endpoint: Subjective ratings of the coupling conditions, for both streaming sound quality and own voice perception (occlusion effect). These will be administered via a 100 point scale, from 0 to 100 (0 = least preferred, 100 = most preferred). For streaming sound quality, participants will be presented with a pop song and will be asked to adjust the volume to their most comfortable level before making a rating. For the own voice perception portion, participants will be asked to read the Rainbow Passage prior to making a rating.

Secondary endpoint: Analysis of audio recordings of participants reading the Rainbow Pas-sage (for occlusion investigation). Given the Lombard effect, researchers believe there to be a possibility that subjects will adapt certain qualities of their voice depending on the level of occlusion. This secondary measure may give insight to such phenomenon and supplement further understanding of the primary objective.

7 Inclusion and Exclusion Criteria

Inclusion criteria:

18+ years of age

Hearing loss must be within the recommended fitting range and candidacy guidelines for the study devices and couplings.

Participants must indicate no prior history of problematic tinnitus or pain/discomfort from loud sounds.

Hearing loss must be symmetrical below 500 Hz (<= 10 dB) and sensorineural etiology Exclusion criteria:

Unable or unwilling to have two appointments lasting approximately 2 hours each

Unable or unwilling to wear devices for study appointments

Active middle or outer ear drainage, infection, redness, swelling within 90 days of appointments

8 Measurements and procedures

Participants will be seen for two appointments. The first appointment will consist of updating the audiogram and taking earmold impressions.

The second appointment will last approximately one hour.

Two sets of comparisons will take place investigating streaming sound quality, and own voice tolerance. To compare streaming sound quality, participants will listen to a streamed music signal under the following conditions – dynamic vent receiver using a custom earmold in the closed position, SDS 4.0 receivers coupled with appropriately fitting open domes, as well as SDS 4.0 receivers coupled with vented domes. Conditions will be counterbalanced and randomized. Participants will listen to a 30 second excerpt of a pop song and make an absolute sound quality rating for each condition. To compare own voice tolerance, participants will read the rainbow passage (Fairbanks, 1960) under the following conditions - dynamic receiver in the open position compared to SDS 4.0 receivers coupled with appropriately fitting vented domes and open domes. Participants will be asked to give an absolute rating for both sets of comparisons-streaming sound quality, and quality of own voice.

All analysis of the results will occur at the conclusion of the study. Paper questionnaires will be digitized for statistical analysis. Audio recordings will be anonymized and saved as .wav files to be used for an intensity analysis. These will be stored on a company network drive.

9 Statistical design and analysis

A power analysis was conducted prior to the investigation. For a repeated measures ANOVA, a sample size of 20 participants is deemed adequate to detect a medium effect size (.3) with a power of 80%. This assumes a nonsphericity correction of 1. In the event that the dataset is not normally distributed, a rational arcsine unit transformation will be performed prior to per-forming the statistical analysis.

10 Investigation Duration

Expected participation for each subject is two days. The entire investigation is expected to last 2-4 weeks.

11 Data handling and management

Electronic or paper based CRFs will be used to capture the participant data. If electronic, subjective questionnaires will be available in the EDC system and the participant will be able to read question and choose answer. If paper based subjective questionnaires are used, the participant will answer each question and the results will be transferred to the EDC by the investigator. Objective data will either be entered in directly to the EDC system, or transferred from a paper based CRF into the EDC system.

All CRFs are kept current to reflect the subject's status at each phase during the course of study. Participants cannot be identified in the CRF by name or initials and birth date but an appropriate coded identification is used. All study team members are authorized for the CRF entries and it is assured that any authorized person can be identified both for pCRFs and eCRFs. If pCRFs are used, the investigator's initials and subject ID are documented and data are entered into an electronic file for analysis by the respective investigator and data will be monitored by the assigned monitor. In case of a self-evident corrections, either the subject does it by himself or the investigator undertakes the correction by crossing out the word/sentence with a single horizontal line and by adding the correction including his personal identifier and the date.

The results for the audiometer-based objective measure will be taken from the computer used to complete the test and imported into the EDC system or transferred via an excel or csv file. Real Ear Measurements will be imported from the verification system and stored as an excel file.

The pCRFs/eCRFs are only available to the local study team and to the monitor of the study. In the case of an audit or a serious adverse event, the CRFs may need to be de-anonymized and sent to the governing body (i.e FDA) or insurance company.

Any paper-based data will be stored in a locked filing cabinet at the investigation site. All electronic data will be stored on an access-restricted server owned, operated, and maintained by Sonova USA. Servers used to store data in this investigation are physically located in the US. Permission to access data will be limited to study manager, monitor, PI, and essential research staff, as designated by the principal investigator.

During data collection of the investigation, physical copies of the data will be compiled and digitized by the study manager/investigator on a daily basis. Data will be reviewed for misentries or inaccuracies as each data set is entered.

The extent and nature of monitoring appropriate for the clinical investigation including the strategy for source data verification (SDV) are based on considerations such as the objective, design, complexity, size critical data points and endpoints of the clinical investigation. A detailed plan for monitoring arrangements is provided separately from this CIP.

12 Amendments to the CIP

Any necessary amendments to the CIP will be communicated to the study manager/sponsor. A new version of the CIP will be written, with the necessary changes and justification, and the PI will be trained on the amendments. The amended CIP will go through the approval process and necessary signatures obtained from the study manager/sponsor, PI, and statistician. The amended CIP will be uploaded to the eQMS system as an additional revision.

13 Deviations from clinical investigation plan

Deviations from the CIP to protect the rights, safety and well-being of human participants under emergency circumstances may proceed without prior approval of the sponsor and the EC – such deviations will be documented and reported to the sponsor representative (Study Manager) and the EC as soon as possible. Apart from that the investigator is not allowed to deviate from this CIP unless that deviation does not influence the investigation data.

14 Device accountability

Sonova, in its capacity as sponsor, will maintain a log of all investigational devices, including the date of shipment from Sonova to the site, serial number, receiving study site, and date returned to Sonova.

The site will maintain a log of the devices provided by Sonova, including the date of receipt, serial number, date of fitting, participant identification, date of return to site by participant, and date returned to Sonova. Sonova will provide each site a template with which to record such information.

If a device needs to be replaced due to a device deficiency, the PI or sub-investigator will add the new device serial number, date of receipt, and date of return of the defective device on the Device Accountability Log.

In the case of a device deficiency, the Adverse Event-Device Deficiency form will be completed by the study manager and the PI or sub-investigators together.

15 Informed consent process

Informed consent will be obtained from participants prior to any study participation in accordance with the IRB guidelines. The participants will be granted sufficient time to read through the consent in full and ask any questions they have before signing. After the participant signs the consent form, the researcher will sign and provide a copy to the participant. This process will take place in a private office located in the Phonak Audiology Research Center (PARC).

Informed Consent will only be obtained by investigation participants who can provide informed consent themselves before enrollment.

16 Adverse events, adverse device effects and device deficiencies

Device deficiencies and all **adverse events (AE)** including all **serious adverse events (SAE)** are collected, fully investigated and documented in the source document and appropriate case report form (CRF) during the entire investigation period, i.e. from participant's informed con-sent until the last protocol-specific procedure, including a safety follow-up period (ISO-14155, 2020). Documentation includes dates of event, treatment, resolution, assessment of serious-ness and causal relationship to device and/or investigation procedure.

Information on AEs is systematically collected during the regular investigation visits, and phone calls (if applicable).

The investigator(s) will follow-up on a biweekly basis with any participant experiencing an AE until either a) the participant reports resolution of the AE or b) 8 weeks have passed since the participant's final visit. If, however, the participant's condition worsens throughout the 8 week follow-up period, the investigator will continue to follow-up biweekly until the AE is resolved or the participant's condition stabilizes over an 8 week period.

The reporting of Serious Adverse Events and Device Deficiencies follows the Regulation (EU) 2017/745 and the MDCG 2020-10/1 Safety Reporting in Clinical Investigations of Medical Devices under Regulation (EU) 2017/745.

The causality assessment of the SAE will be conducted according to MDCG 2020-10/1 Safety Reporting in Clinical Investigations of Medical Devices under Regulation (EU) 2017/745.

17 Vulnerable populations

This investigation will not include any vulnerable populations.

18 Suspension or premature termination of the clinical investigation

The study will be terminated if the majority of the participants are not able to wear the devices for the study visit.

The study will be terminated if the participants or researchers are exposed to safety risks other than those outlined in this document.

The study may be terminated in the event natural disasters, widespread outbreak of illness, compromised structure of the investigation site, etc. that would make continuation of the study impossible or impractical. The study will be suspended within 5 days of determination that the study or device put participants at an unreasonable risk.

If a participant is suspended, terminated, or withdraws from the study, their data can be traced with their unique study identification number.

According to the FDA, follow-up is required for participants who experience Serious Adverse Events. Follow up will be conducted by the study manager and/or the PI until the nature of the event is resolved.

19 Publication policy

The clinical investigation will be registered in clinicaltrials.gov, a publicly accessible database, as required by U.S. regulations.

The results of the clinical investigation will be published on clinicaltrials.gov no later than one calendar year following the final participant appointment.

An internal report of the results of this investigation will be completed and uploaded to eQMS.

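### Does section 4's participant-blinding statement need limiting because only the dynamic streaming condition is worn in a custom earmold?

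*Combined protocol and SAP*

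**What the plan says.** Section 4 (Design of the clinical investigation) says that "the participants will be blinded to the conditions". Neither that section nor any other says what is withheld from participants, by what means, or whether blinding is checked.

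Section 8 (Measurements and procedures) gives the first two streaming conditions as "dynamic vent receiver using a custom earmold in the closed position, SDS 4.0 receivers coupled with appropriately fitting open domes". The third condition uses the same SDS 4.0 receivers, this time with vented domes. On order it says: "Conditions will be counterbalanced and randomized". On the visit before the ratings it says: "The first appointment will consist of updating the audiogram and taking earmold impressions".

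Section 6 (Endpoints) makes the primary endpoint "Subjective ratings of the coupling conditions, for both streaming sound quality and own voice perception", each scored by the participant from 0 to 100. Section 2 (Objectives) gives one hypothesis for streaming: "a dynamic venting system will provide better streaming sound quality than coupling achieved with an open dome". Section 1 (Background) explains the choice of comparators: "previous research has investigated custom earmolds with various degrees of venting as comparators to a dynamic venting system", whereas universal domes are customary in the United States, and this study sets the dynamic system against them.

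**The concern.** The participant is the one who scores the outcome, so participant blinding is the blinding that matters for this endpoint. Within the streaming task, wearing an earmold and wearing the dynamic device always go together. Every participant wears all three couplings, so each has a direct comparison between an earmold and a dome, and each has already had impressions taken. It is plausible that many could tell the two apart by feel. Counterbalancing and randomization govern the order of the conditions and do not disguise what is in the ear.

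If a participant recognised the earmold, took it to be the device under test and rated it more generously (or more harshly) for that reason, the shift would fall on the hypothesised contrast between the dynamic system and the open dome. Section 4 calls the study confirmatory, and section 19 commits to posting the results publicly. A reader told without qualification that the ratings were blinded might then give the streaming result more weight than the described procedures support.

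**Working it through.** The plan gives no figure for blinding, so the check compares what the sections establish with what the concern needs.

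**Streaming conditions (section 8)**

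| Condition | Receiver | Coupling |
|---|---|---|
| D | dynamic, vent closed | custom earmold |
| O | SDS 4.0 | open dome |
| V | SDS 4.0 | vented dome |

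Three conditions give 3 × 2 / 2 = 3 pairwise contrasts. D−O and D−V set an earmold against a dome; O−V does not. So 2 of 3 streaming contrasts are exposed, and D−O is the one hypothesised in section 2. Streaming is 1 of the 2 tasks in the primary endpoint. For the own-voice task, section 8 does not name the coupling worn with the dynamic receiver, so nothing is concluded there.

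These counts show only that one condition of three uses an earmold. That is the comparison the study means to make: the dynamic system as worn, against domes. The counts carry no information about whether blinding holds.

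**What a bias would require.** Write the observed mean difference D−O as the true difference plus δ, where δ is the shift due to recognition. For δ to differ from zero, four steps must all occur:

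1. The participant can tell earmold from dome. Plausible, but not stated in the documents.
2. The participant links the earmold to the device under test. Not stated; no section says what participants are told the impressions are for.
3. The participant holds an expectation about that device. Not stated; the direction in section 2 is the researchers' hypothesis, and nothing shows that it is shared with participants.
4. The expectation moves the 0–100 rating. Not stated.

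The documents give neither the size nor the sign of δ, so no error rate or bias can be calculated.

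**Two readings of section 4**

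- *Not told which condition is being worn.* Sections 4 and 8 are consistent. Withholding the label is possible whatever the couplings feel like.
- *Unable to tell the conditions apart.* Section 8 would then need a masking procedure, and none is described. But section 4 does not make this stronger claim.

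**What a change would alter.** Rewording section 4 changes no condition, rating, contrast or test. The one calculation in the plan is the sample size in section 9, and blinding does not enter it. For completeness, it reproduces: with f = 0.3, m = 3 conditions, n = 20, nonsphericity correction 1, and assumed α = 0.05 and correlation ρ = 0.5 (the plan states neither), λ = f²·n·m/(1−ρ) = 0.09 × 20 × 3 / 0.5 = 10.8 on 2 and 38 degrees of freedom. Power is 0.814, and 20 is the smallest n that reaches 80%. Over the unstated ρ, the required n is 38 (ρ = 0), 27 (0.3), 20 (0.5) and 13 (0.7). None of these figures depends on blinding.

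A change of substance, such as putting the comparators in earmolds too, would give up the dome comparison and go back towards the earmold comparators that section 1 says earlier work has already covered.

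**The case for a change.** The best argument for acting is that the remedy is nearly free. If the sponsor means only that participants are not told which coupling they wear, saying so costs one sentence and removes an ambiguity. If masking cannot be done because the couplings differ physically, that is a reason to limit the claim. An overstated design feature can also be corrected without first estimating the bias it might hide.

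Much of this stands. The facts are right: the statement in section 4 is unqualified, the earmold is named only for the dynamic streaming condition, and no masking or blinding check is described. Describing the method would be good practice when the results are written up.

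It does not amount to a change in the plan, for two reasons. First, a sentence confining blinding to not being told the condition would assert something the documents do not say. If the site uses some masking at insertion, the sentence would be false, and placed in section 4 it would also cover the own-voice task, where the coupling is not specified. Second, the sentence would neither reduce a bias nor measure one. The ratings would be collected and analysed exactly as before. A reader with section 8 can already see that the couplings differ physically and can weigh the blinding statement accordingly.

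**Conclusion.** No change follows. The documents establish a gap in description: section 4 claims participant blinding without saying to what or how. They do not establish that the claim is wrong, because that depends on recognition by feel and then an expectation that moves the rating, and neither is documented. The reach, if those steps did occur, is 1 of 2 primary tasks and 2 of 3 streaming contrasts; the size and direction of any effect are unknown. Rewording would change none of the plan's figures or analyses.

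This rests on the ordinary reading of blinded as not being told which coupling is worn, and on nothing in the documents showing that participants are given the hypothesis. It would need another look if participants were told which device is expected to do better, or if the results were reported as though the couplings could not be told apart. Short of that, whoever reports the study can state what participants were told and how the devices were fitted. The physical difference between earmold and dome comes with the comparison the study was designed to make.

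### Coupling order is counterbalanced, but section 9 names no presentation-position term; adding one costs almost nothing and protects power if ratings drift

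*Combined protocol and SAP*

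**What the plan says.** Order is controlled by design in two places. Section 4 states: "The order of conditions will be counterbalanced and the participants will be blinded to the conditions". Section 8, in the description of the streaming comparison, adds: "Conditions will be counterbalanced and randomized". Section 4 speaks of conditions in general, so the point applies to the own-voice task as well. No order scheme (all six orders, or a three-order Latin square) is named.

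Each participant rates three couplings in succession in each task. For streaming: "Participants will listen to a 30 second excerpt of a pop song and make an absolute sound quality rating for each condition". For own voice, the same passage is read aloud under each coupling.

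Section 9 names the analysis only inside the power statement, as a repeated measures ANOVA for which "a sample size of 20 participants is deemed adequate" at 80% power, with effect size .3 and a nonsphericity correction of 1. No section mentions a position, period, order or sequence term, and none excludes one. On enrolment, section 4 says: "The sample population will be of 15-20 human subjects".

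**The concern.** Counterbalancing spreads any drift common to all participants (practice, fatigue, a settling use of the 0-100 scale) about evenly over the three couplings. That keeps the coupling means comparable, but it does not remove the drift from the data. In an ANOVA with coupling as the only within-participant factor, the drift appears as scatter within participants and inflates the error mean square. The F test then becomes conservative and loses power. A position factor removes that scatter.

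The study is small, calls itself confirmatory, and is only just above 80% power at the top of its enrolment range under the assumptions below. There is little power to give away.

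**Working it through.** **Inputs from the documents.** Three couplings per task (sections 4 and 8); N = 20, effect size .3, 80% power, nonsphericity correction 1 (section 9); 15 to 20 participants (section 4).

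**Assumptions.** Effect size read as Cohen's f; alpha .05; correlation .5 between a participant's ratings; drift D = shift from first to third position, in SDs of a rating, split as -D/2, 0, +D/2. None of these is stated in the documents, so a range of D is shown.

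**1. Reproduce the planned sample size.** Noncentrality λ = f²·N·m/(1 − ρ) = .09 × 20 × 3/.5 = 10.8, with 2 and 2 × 19 = 38 df. Power is 81.4%. N = 19 gives 79.1%, so 20 is the smallest N that reaches 80%, matching the plan.

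**2. Cost of a position term when there is no drift.** Three positions use 2 df, leaving 36.
- Position exactly orthogonal to coupling: λ is unchanged and power is 81.2%. N = 19 gives 78.9%, so the minimum N is still 20.
- Six orders used as evenly as 20 participants allow (three full sets plus two orders): power is 81.1%.

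The minimum N is also the same in both models at correlations of 0, .3 and .7 (38, 27 and 13). The planned N therefore does not reveal whether a position term was intended.

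**3. Cost of omitting it when there is drift.** Each participant's position effects have sum of squares D²/2. With balanced orders, the error mean square rises by N(D²/2)/[2(N − 1)] = D²N/[4(N − 1)]. At N = 20 and D = .5 this is .25 × 20/76 = .0658. Against a within-participant error variance of .5, that is 13.2%. It is 13.1% once the leftover imbalance at N = 20 is allowed for, because a little of the drift falls on coupling instead.

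Power then comes from the doubly noncentral F for the coupling-only model and the noncentral F for the model with position. Coupling means are equally spaced (spread .6/√(2/3) = .735 SD), and results are averaged over the possible incomplete sets of orders.

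| Drift D (SD) | Rise in error variance, N = 20 | Type I error, coupling only, N = 20 | Power N = 20, without / with position | Power N = 15, without / with position |
|---|---|---|---|---|
| 0 | 0% | 5.0% | 81.4% / 81.1% | 67.3% / 66.5% |
| .25 | 3% | 4.6% | 80.3% / 81.1% | 65.8% / 66.5% |
| .5 | 13% | 3.6% | 76.7% / 81.1% | 61.3% / 66.5% |
| .75 | 30% | 2.4% | 70.6% / 81.1% | 54.0% / 66.5% |

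The last row is an extreme: the drift is about as large as the whole assumed coupling spread.

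**4. Break-even.** The two models have equal power at D = .138 SD for N = 20, .109 for N = 18 and .177 for N = 15.

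**5. Bias.** With six orders at N = 20, the worst case is two leftover orders that both put one coupling ahead of another, by one position and by two. The shift in that difference is (D/2 + D)/20 = .075D. With a three-order Latin square it is (D/2 + D/2)/20 = .05D. At D = .5 these are .0375 and .025 SD. A simulation of 20,000 trials at N = 20 and D = .5 gave a mean bias of −.001 SD and power of 77.1% without and 81.3% with position, in line with the table.

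**The case against.** **Section 9 never writes out a model.** It does not even list coupling as a factor, so faulting one absent term could be called preference, and the wider gap is the unspecified model. That is fair as far as it goes, and it is why no error is claimed. But position is the factor the design already controls, so naming it is a specific improvement.

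**Drift may be negligible.** Three short ratings may not drift much. At .25 SD the gain is only .8 points, and a gain above 4 points needs about .5 SD. This stands: the benefit is conditional on an assumed quantity.

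**The low cost depends on near-balanced orders.** If each participant's order were drawn independently, simulation at N = 20 gives, without and with position, 81.6% and 78.9% with no drift, 79.9% and 78.5% at .25 SD, and 76.4% and 79.3% at .5 SD. The term would then lose at small drift. The arithmetic is right, but the stated counterbalancing excludes that scheme.

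**The power figures are for the omnibus F test.** The hypotheses in section 2 are two specific pairwise comparisons. This limits the figures to one test and one pattern of means. The direction carries over, because those comparisons use the same error term.

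**Carryover is not covered.** A position term handles drift common to all participants, not the effect of one coupling on the rating of the next. That limit is accepted.

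**Conclusion.** The point holds as a low-priority improvement in efficiency. The design controls order, the named analysis does not mention it, and a coupling-only ANOVA would be conservative if ratings drift. At N = 20 with near-balanced orders, including position costs .2 to .35 points of power when there is no drift. It recovers .8, 4.4 and 10.5 points at drifts of .25, .5 and .75 SD. At N = 15 it costs .8 points with no drift and recovers about 5 points at .5 SD. The coupling comparison is not materially biased either way.

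These sizes rest on alpha .05, correlation .5, f = .3 with equally spaced means, and a linear drift common to all participants.

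**What to change.** State in section 9 that, for each task, the model has coupling and presentation position (1 to 3) as fixed effects and participant as a random effect. Take the coupling comparisons from that model: dynamic vent versus open dome for streaming, and dynamic vent versus vented dome for own voice. Make sure the case report form records the position of every rating.

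Optionally, say that orders are assigned in randomised blocks of the six orders or of a three-order Latin square. Neither divides 20 exactly, but the position term adjusts for the small remainder, and blocking secures the near-balance on which the low cost depends.

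The cost is one sentence in section 9, one recorded field if it is not already captured, and 2 error degrees of freedom. The planned sample size does not change.
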